9.3.2. Analysis for Laboratory Parameters

Laboratory data from all central and local laboratories will be included in analyses. Different laboratories are likely using slightly different normal reference ranges, which should not affect the planned analysis since they are all categorical and reported based on CTCAE toxicity grade or relationship to the normal ranges. The default convention for reporting of laboratory units will be standard international (SI) units. If a lab value is reported using an inequality symbol e.g., less than (<) a certain value, or greater than (>) a certain value, the given numeric value will be used in the summary. Data will be presented in listings with their inequality symbol.

For each parameter in the clinical chemistry and hematology laboratory group, respectively, CTCAE toxicity grading is used to classify patients into a toxicity grade from 1 to 5 (where

applicable) for each timepoint assessment. The number and percentage of patients with highest grade during the treatment period will be summarized for each grade from 1 to 4 and Grade 3-4, along with such summary for the value collected at baseline.

For the laboratory parameters that cannot be classified by CTCAE grade, the number and percentage of patients in the categories of treatment-emergent low or treatment-emergent high based on the normal reference range associated with the parameter will be summarized.

The number and percentage of patients in each category of abnormal hepatic laboratory values will be summarized.

Laboratory parameters will be listed by the group of chemistry, hematology, and urinalysis. In the data listing, flags that indicate the corresponding CTCAE grades and the classifications relative to the laboratory reference ranges will be included. In addition, a separate listing will be prepared for patients who met Hy's law, if any.

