OS is defined as the time (months) from the date of first dose of study drug to the date of death for patients who died in the study due to any cause, and the time to the last contact date known to be

G1T28-213

alive for those patients who survived as of the date for final database lock (censored cases). OS will be conducted at the time when approximately 70% of patients (~32 patients) have died. Kaplan-Meier plots will be produced. The median, 25th percentile, and 75th percentile of OS will be estimated using the Kaplan-Meier method with their corresponding 95% CI calculated based on the method by Brookmeyer and Crowley (1982). OS will be analyzed on the FAS.

Analysis for myelosuppression endpoints:

The myelosuppression endpoints include the occurrence of severe neutropenia (SN). SN is defined as the absolute neutrophil count (ANC) laboratory value that meets the National Cancer Institute Common Terminology Criteria for Adverse Events (NCI-CTCAE) v5.0 criteria for  $\geq$  Grade 4 toxicity (i.e., ANC < 0.5 x 10 $^9$ /L in SI Unit). The number and percentage of patients with at least one occurrence of SN during the treatment period will be summarized. For counting myelosuppression endpoints (e.g., the number of red blood cell [RBC] transfusions on/after Week 5, and the number of dose reductions during the treatment period), the total number of the event, the total duration of treatment period (either in the unit of weeks or cycles), and event rate per 100 weeks or cycles will be summarized. For example, the event rate for RBC transfusions on/after Week 5 will be reported per 100 weeks and that for dose reduction will be reported per 100 cycles. For a given event, patients without any events during the treatment period will be assigned a value 0 to be included in the analysis.

Analysis for safety endpoints

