8.1.4. Secondary Efficacy Endpoint – Myeloprotection Efficacy Endpoints

Secondary myeloprotection endpoints that are defined to assess trilaciclib's effect on multiple lineage protection during the treatment period are described in Table 7 by lineage (i.e., neutrophils, and red blood cells [RBCs]). Endpoints that evaluate trilaciclib's impact on study drug delivery during the treatment period are also described in Table 7.

Unless otherwise specified, all endpoints described in Table 7 are derived based on data collected through scheduled and unscheduled visits during the treatment period.

Lineage	Endpoint	Type of Variable		
Neutrophils	Occurrence of severe neutropenia (during cycles 1/2 and overall study)	Binary		
	Occurrence of febrile neutropenia			
	Occurrence of G-CSF administration	Binary		
RBCs	Occurrence of Grade 3 or 4 decreased hemoglobin	Binary		
Dose Modifications	Occurrence of SG dose reduction	Binary		
	Number of SG dose reductions (event rate per 100 cycles)	Counting		
	Occurrence of cycle delay due to hematologic toxicity	Binary		
	Number of cycle delays due to hematologic toxicity (event rate per 100 cycles)	Counting		

Table 7Myeloprotection Endpoints

G-CSF=granulocyte colony stimulating factor; RBC=red blood cell, SG= sacituzumab govitecan-hziy..

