8.1.4.1. Neutrophil-Related Endpoints

Occurrence of Severe Neutropenia (during Cycles 1/2 and overall study)

Occurrence of Severe Neutropenia (Grade 4 neutropenia) for a patient is defined as having as least one ANC value $< 0.5 \times 10^9$ /L among all ANC measurements regardless of scheduled or unscheduled visits. Occurrence of Severe Neutropenia is a binary random variable (Yes or No).

Occurrence of Febrile Neutropenia

FN is an AE as reported by the Investigator and captured in the eCRF. A PT term of FEBRILE NEUTROPENIA is used to identify a FN event. The occurrence of FN for a patient is defined as having at least one FN event and is a binary random variable (Yes or No).

Occurrence and Number of Granulocyte Colony Stimulating Factor (G-CSF) Administrations

Administration of G-CSF is collected throughout treatment period. Cycles where G-CSF was administered will be identified by comparing the start and stop dates of each administration of G-CSF to cycle interval. If any of the time intervals in which G-CSF was administered overlapped with any dates between the start of a cycle and the end of the cycle, that cycle will be considered as having a G-CSF administration. Data handling conventions for missing start and stop dates are described in Section 5.4.

The occurrence of G-CSF administration for a patient is defined as having at least one cycle in which G-CSF was administrated for the patient. It is a binary random variable (Yes or No).

The number of cycles with G-CSF administrations for a patient is the total number cycles where the patient received at least one dose of G-CSF. For patients who did not have any G-CSF use and those who were enrolled but did not receive any study treatment, the value of 0 will be assigned.

8.1.4.2. **RBC-Related Endpoints**

Occurrence of Grade 3 or 4 Decreased Hemoglobin

Occurrence of Grade 3 or 4 decreased hemoglobin (Hgb) for a patient is defined as having at least one Hgb value that was < 8.0 g/dL among all scheduled or unscheduled assessments. It is a binary random variable (Yes or No).

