9.3. Clinical Laboratory Data

9.3.1. Laboratory Parameters

Blood and urine samples for the determination of clinical chemistry, hematology, and urinalysis laboratory variables described in Table 9 will be measured according to Schedule of Assessments in Appendix 1.

Lab Category	Lab Parameters
Chemistry	albumin, alkaline phosphatase (ALP), total bilirubin, calcium, chloride, creatinine, glucose, inorganic phosphorus, potassium, total protein, alanine aminotransferase (ALT), aspartate aminotransferase (AST), lactate dehydrogenase (LDH), sodium, blood urea nitrogen (BUN)
Hematology	hemoglobin, white blood cell (WBC), platelet counts, absolute neutrophil count (ANC), absolute lymphocyte count (ALC)
Urinalysis	semiquantitative dipstick: specific gravity, pH, evaluation of glucose, protein, bilirubin, ketones, leukocytes, and hemoglobin microscopic examination, including red blood cell (RBC), white blood cell (WBC), and casts will be performed, if necessary

 Table 9
 Laboratory Categories and Parameters

Lab = laboratory.

For hematology parameters, if absolute counts are not provided, those values will be derived from the differential counts by multiplying differential value with leukocyte value from the same sample. The normal ranges will be left missing in those cases.

Clinical chemistry and hematology assessments will be graded according to NCI CTCAE criteria, Version 5.0 or later. The determination of CTCAE grade for each measurement will be based on the collected laboratory values and will not involve clinical judgement. For laboratory parameters that CTCAE toxicity grade are not available, they will not be included in the analyses in which toxicity grades are reported. Instead, these parameter results will be classified and reported by the low/normal/high based on the laboratory normal reference ranges.

Abnormal Hepatic Laboratory Values

Abnormal hepatic laboratory values are defined in the following categories including any occurrence among all on-treatment, post-baseline assessments including scheduled and unscheduled values.

- Hy's Law:
 - Alanine aminotransferase (ALT) and/or aspartate aminotransferase (AST) > 3x the upper limit of normal (ULN), alkaline phosphatase (ALP) < 2xULN, and total bilirubin ≥ 2xULN
 - Preexisting baseline ALT, AST, OR total bilirubin values above the upper limit of normal, and the patient subsequently presents with:

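### Replacing a laboratory result of `<x` by x misclassifies results whose reporting limit equals a strict cut-off (ANC `<0.5`, hemoglobin `<8.0`)

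*SAP*

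**What the plan says.** SAP 9.3.2 covers results that carry an inequality sign. For any parameter, and for either direction of the sign, "the given numeric value will be used in the summary". The sign itself survives only in the listings: "Data will be presented in listings with their inequality symbol". The same section describes the planned laboratory analyses as categorical, based on CTCAE grade or on position relative to the normal range. SAP 10 removes the change-from-baseline laboratory summaries from the abbreviated report.

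SAP 9.3.1 says of grading: "The determination of CTCAE grade for each measurement will be based on the collected laboratory values". It adds that no clinical judgement enters.

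SAP 8.1.4.1 defines SN as at least one ANC strictly below 0.5 x 10^9/L, "among all ANC measurements regardless of scheduled or unscheduled visits". The synopsis of the protocol uses the same strict limit. SAP 8.1.4.2 defines Grade 3 or 4 decreased hemoglobin as at least one value strictly below 8.0 g/dL. SAP 8.1.4 says that these endpoints are "derived based on data collected through scheduled and unscheduled visits during the treatment period". Nothing in 8.1.4 says how to treat a value that carries an inequality sign, and it does not refer to 9.3.2.

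**The concern.** A result of `<0.5` is known to be below 0.5. Once it is replaced by 0.5 it is no longer below 0.5, so a certain Grade 4 value is tabulated as something less. The rule is not needed for a mean or a median here, because 9.3.2 plans no continuous laboratory summary. It operates only where losing the sign can change a patient's class.

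For low-count endpoints the error has one direction. Replacing `<x` by x can raise the analysed value but never lower it, so it can remove an SN or Grade 3/4 hemoglobin event but never add one. The study has one arm, so there is no control group with the same error. The context the protocol gives for SN is an external figure, the 14% Grade 4 neutropenia cited for sacituzumab govitecan in Protocol 4.2.3. SN is also one of the myeloprotection endpoints that remain after SAP 10 dropped six items.

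**Working it through.** The plan states no figure on this point, so there is none to reproduce. The check applies the rule and then the test.

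**Inputs.**
- Substitution of `<x` by x: SAP 9.3.2.
- SN test, value < 0.5: SAP 8.1.4.1 and the protocol synopsis.
- Hemoglobin test, value < 8.0: SAP 8.1.4.2.
- N = 30: SAP 1.3. This assumes that all 30 enrolled patients were dosed and are in the full analysis set.
- Reporting limits: not in the documents, so a range is tried.

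**Step 1. Substitute, then test.**

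| Reported result | Value used | Meets criterion after substitution? | True status |
|---|---|---|---|
| ANC `<0.1` | 0.1 | Yes | Certainly yes |
| ANC `<0.2` | 0.2 | Yes | Certainly yes |
| ANC `<0.3` | 0.3 | Yes | Certainly yes |
| ANC `<0.4` | 0.4 | Yes | Certainly yes |
| ANC `<0.5` | 0.5 | **No** | **Certainly yes** |
| ANC `<1.0` | 1.0 | No | Unknown |
| Hgb `<7.0` | 7.0 | Yes | Certainly yes |
| Hgb `<8.0` | 8.0 | **No** | **Certainly yes** |

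The rule gives a demonstrably wrong class only where the reporting limit equals the cut-off.

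**Step 2. Effect of one patient.** A patient is lost only if no other value in the treatment period meets the criterion. Each such patient lowers the rate by 1/30 = 3.3 percentage points.

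**Step 3. Illustration.** Take the 14% cited in Protocol 4.2.3 as the rate: 0.14 x 30 = 4.2, or about 4 patients. Suppose 0, 1 or 2 of them are missed; this range is an assumption. Intervals are Clopper-Pearson 95%.

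- None missed: 4/30 = 13.3% (3.8 to 30.7)
- One missed: 3/30 = 10.0% (2.1 to 26.5)
- Two missed: 2/30 = 6.7% (0.8 to 22.1)

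**Step 4. After the fix.** With `<x` classified as below x, the two bold rows change to Yes. The other certain rows keep their class, and ANC `<1.0` is flagged as indeterminate.

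**The case against.** The case against making much of this is strong, and most of it stands.

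- **Reach.** The rule sits in the safety laboratory section and speaks of the summary. SAP 8.1.4 does not cite it, and SAP 9.3.1 bases grades on collected values, where a collected `<0.5` still has its sign. Applying the rule to the SN endpoint is an inference. It is a reasonable one, since 9.3.2 holds the only such rule in the SAP, but the direct effect is on the grade tables of 9.3.2.
- **Occurrence.** No document gives a reporting limit for ANC or hemoglobin, or says that any laboratory reports `<0.5`. Protocol 11.3.5 and 17.1 place testing at local laboratories, while SAP 9.3.2 mentions central and local ones; neither settles the limits.
- **Rescue by other samples.** One numeric value below the cut-off is enough. Hematology is scheduled on Day 1 and Day 8, with weekly repeats during delays for hematologic toxicity.
- **Visibility.** The laboratory listings keep the sign and show the grade, so a case could be found by eye. SAP 8.2.4 plans no listings for the myeloprotection endpoints themselves.
- **Use.** These endpoints are reported as counts and percentages, with no test or decision rule.

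A reader might infer that the lowest counts are the ones missed. Step 1 shows otherwise: `<0.1` to `<0.4` are all counted. A reader might also infer that the rule always lowers the SN rate. It can only lower it, but it leaves it unchanged unless an affected result occurs and decides a patient's status.

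A further inference might be that the derivation rule in SAP 9.3.1, "if absolute counts are not provided, those values will be derived from the differential counts", hides cases in the same way when the white cell count is below 0.5 and no differential exists. That rule recovers data. Such a sample is hypothetical, because ANC is a protocol-specified test and is needed for dosing, and it would be ordinary missing data under the SAP's stated policy of no imputation.

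**Conclusion.** The point holds as a minor classification error. SAP 9.3.2 as written gives the wrong class to a result whose reporting limit equals a strict cut-off. This applies directly to ANC `<0.5` in the Grade 4 table. If the rule is carried into SAP 8.1.4.1 and 8.1.4.2, it also applies to SN and to Grade 3/4 hemoglobin `<8.0`.

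The size is 3.3 percentage points per affected patient, always towards a lower rate. The number affected is not in the documents and may be zero. In the illustration the confidence intervals overlap widely, so the issue is correct classification and not a changed conclusion. The documents do not support a claim that the SN result is materially biased in favour of trilaciclib.

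**What to change.** State in SAP 9.3.2, 8.1.4.1 and 8.1.4.2 that, for CTCAE grading and threshold endpoints, `<x` is classified as below x and `>x` as above x. ANC `<0.5` then counts as SN and hemoglobin `<8.0` as Grade 3/4. Flag results whose class cannot be determined, such as ANC `<1.0`, and report how many patients have such a result and no qualifying one. Use the bare numeric value only for any continuous summary.

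Do not substitute an invented number such as x minus one reporting unit. That unit is undefined, and ANC `<1.0` would then be classed as not SN although its status is unknown.

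The cost is a sentence in each of three sections and a derivation flag in the laboratory dataset. No new data are needed, because the sign is already kept for the listings.

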4.3. Definitions for Analysis Related Timepoint and Time Interval

Timepoint and time intervals related to efficacy and safety data collected during the treatment period will be summarized. For each specific category of data, the time interval by which the data will be analyzed or summarized will be specified in the respective section in which the data analysis plan is described.

To clarify data inclusion for each time interval of interest and baseline or end values for each given time interval, Table 3 presents definitions for timepoints, timepoint related assessments, and time intervals involved in statistical data analysis or summary.

Table 3Definitions for Timepoints, Timepoint Related Assessments and Time
Intervals

Term	Definition
Start of study (date)	Date of first dose of any study drug
Study baseline (assessment)	The last non-missing value prior to or on the date of the first dose of any study drug at the time that is before the time of the first study drug administration. If the event occurs on the same day as date of first dose of study drug but does not have the exact time captured, the event is assumed to have occurred prior to the first dose of study drug.
Day 1 of Cycle X (date)	The date when the first dose of any study drug for cycle X is administered. Day 1 of Cycle 1 (C1D1) is the same as the start of study.
End of a cycle (date)	It is defined as Day 1 of the subsequent cycle if the cycle is not the last cycle. For the last cycle, it is defined as the date of the End of Treatment Visit (ETV). If the ETV does not occur for a patient, End of the last cycle will be defined as 14 days post the last dose of any study drug.
Duration of a cycle (days)	Total number of days from Day 1 of the cycle to End of the cycle. That is, End of the cycle $-$ Day 1 of the cycle $+$ 1.
Duration of study drug exposure (weeks)	The total number of weeks from Day 1 of Cycle 1 to the End of the last cycle in the study. That is, (End of the last cycle –Day 1 of Cycle $1 + 1$) / 7.
Duration of total follow-up (months)	The total number of months from Day 1 of Cycle 1 to either the date of death or last contact date in the study known alive, inclusive. That is, duration of total follow-up=(date of death or date of last contact date known alive – Day 1 of Cycle $1 + 1$)/30.4375.

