9. SAFETY ANALYSIS

9.1. General Consideration of Safety Analysis

Safety data summaries will be based on the safety population as defined in Section 3.3 of this SAP.

Safety data collected during treatment will be summarized at the final analysis.

Safety and tolerability will be assessed by AEs, laboratory tests, vital signs and ECG. Safety data will be summarized using descriptive statistics for all patients when appropriate. All safety data collected through scheduled and non-scheduled visits during the treatment period will be included in the safety data analyses. The treatment period for a patient is defined as the time interval from date of C1D1 to the date of End of Treatment (EOT) visit. If the EOT visit does not occur for the patient, then 14 days post the last dose in the last cycle will be used as the end date of treatment. Missing safety data will generally not be imputed, unless otherwise specified.

Baseline assessment is, in general, defined as the last non-missing observation prior to receiving the first dose of any study drug.

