10. CHANGES FROM THE PROTOCOL

- Approximately 45 patients were planned to be enrolled per Protocol Version 2.0. The sponsor decided to close enrollment to this study on February 14, 2023 in order to reallocate resources to other ongoing trilaciclib clinical trials. The final total number of patients enrolled in this study is 30.
- The protocol has defined two planned analyses. The first planned analysis, analyses for progression free survival, tumor response endpoints, and myeloproctection endpoints, were to be conducted when approximately 80% of the patients have radiographically determined disease progression or have died. The final planned analysis is to be conducted when approximately 70% of patients have died. The first planned analysis was not officially conducted as planned and was combined with the the final planned analysis (see Section 2.1).
- The following secondary objectives, intended to evaluate the myeloprotective effects of Trilaciclib when administered prior to SG, were not conducted as part of the final analysis as they were not deemed critical for the aCSR:
 - o Occurrence and number of RBC transfusions on/after Week 5
 - Occurrence of ESA administration
 - Occurrence of Grade 3/4 decrease of platelets
 - Occurrence and number of platelet transfusions
 - Occurrence of serious infections
 - Use of IV antibiotics
- The protocol mentions the collection of ECOG performance status information. The summary and listing of these data was deemed non-critical and will not be included for the aCSR.
- The change from baseline summaries for laboratory assessment will not be included for the aCSR.

G1 Therapeutics

11. **REFERENCES**

Wu, Jianrong. Sample size calculation for the one-sample log-rank test. Pharmaceutical Statistics. 2015;Volume 14:26-33.

G1 Therapeutics

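### Highest lab grade is taken over a period that can include the pre-dose C1D1 sample, and no planned table shows within-patient worsening

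*SAP*

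**What the plan says.** **Graded labs.** SAP 9.3.2 summarizes chemistry and hematology by each patient's highest grade: "The number and percentage of patients with highest grade during the treatment period will be summarized for each grade from 1 to 4". The sentence goes on to add Grade 3-4 and a matching baseline summary: "along with such summary for the value collected at baseline".

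**The period.** SAP 9.1 gives the treatment period as "defined as the time interval from date of C1D1 to the date of End of Treatment (EOT) visit", and adds: "All safety data collected through scheduled and non-scheduled visits during the treatment period will be included in the safety data analyses". The lower limit is a date, not the time of the first infusion.

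**Baseline.** SAP Table 3 (section 4.3) takes "The last non-missing value prior to or on the date of the first dose of any study drug", provided it precedes the first administration. A same-day record without a time is assumed to be pre-dose.

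**Other safety data.**
- Ungraded labs are counted as "treatment-emergent low or treatment-emergent high based on the normal reference range associated with the parameter" (SAP 9.3.2).
- Abnormal hepatic categories use on-treatment, post-baseline values (SAP 9.3.1).
- Vital signs use measurements after the first dose (SAP 9.4.1), and ECG findings use post-baseline assessments (SAP 9.5.1).
- AEs must occur or worsen after the first dose (SAP 9.2.1).

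**What was dropped.** SAP 10 states: "The change from baseline summaries for laboratory assessment will not be included for the aCSR".

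**Hemoglobin endpoint.** SAP 8.1.4.2 counts a patient with "at least one Hgb value that was < 8.0 g/dL among all scheduled or unscheduled assessments".

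**The concern.** Graded chemistry and hematology are the exception among the SAP's safety rules, and no reason is given. Two things follow.

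First, a value obtained before any study drug can enter the on-treatment column. Whether it does depends on scheduling, so two patients with the same course can be reported differently.

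Second, the table does not measure change within patients. SAP Table 1 lists changes in laboratory parameters and Grade 3 or 4 chemistry abnormalities among the safety endpoints. Protocol 12.4.7.2 planned change-from-baseline summaries and grade summaries by cycle as well as overall. SAP 10 removes the former, and SAP 9.3.2 describes only the overall treatment period. The highest-grade table is therefore the main laboratory summary left. The patients are pretreated and there is no control arm, so separating abnormalities that came in with the patient from those that arose on treatment relies on each patient's own baseline.

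**Working it through.** The plan states no figure for this rule, so there is nothing to reproduce. The check compares the rules and then works through their effect at the final sample size, n = 30 (SAP 1.1).

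**1. When the pre-dose sample counts.** Protocol 11.3.5 allows hematology up to 24 hours and chemistry up to 72 hours before a time point.
- Drawn on C1D1 before dosing: it is baseline, and it is dated inside the period.
- Drawn earlier in the window: it can be baseline, but it is dated outside the period.

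**2. Effect of draw day (assumed counts).** Suppose 3 of 30 patients have Grade 3 lymphopenia before dosing and only lower grades afterwards, while 3 others newly reach Grade 3.
- Samples drawn on C1D1: the treatment-period Grade 3-4 row is (3 + 3)/30 = 20%, and the baseline row is 3/30 = 10%.
- Samples drawn the day before: the treatment-period row is 3/30 = 10%, and the baseline row is again 10%.

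The patients are the same, but the treatment-period rate differs by 10 points. In general the addition is k/30, where k is the number of patients whose C1D1 pre-dose grade is Grade 3-4 and who have no Grade 3-4 value afterwards: 1/30 = 3.3%, 3/30 = 10%, 6/30 = 20%. All values of k are assumptions.

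**3. What the baseline column recovers.** If every baseline sample lies in the period, each patient's highest grade is at least the baseline grade. For any grade g:

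(period count at ≥g) − (baseline count at ≥g) = number newly reaching ≥g.

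In step 2 with C1D1 samples this gives 6 − 3 = 3, which is correct. With samples from the day before it gives 3 − 3 = 0, although 3 patients newly reached Grade 3.

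**4. What it cannot recover.** Take a simulated cohort of 30 with baseline samples in the period.

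| Grade at least | 1 | 2 | 3 | 4 |
|---|---|---|---|---|
| Baseline | 10 | 5 | 0 | 0 |
| Highest in period | 22 | 14 | 7 | 1 |
| Difference | 12 | 9 | 7 | 1 |

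Seventeen patients in this cohort worsened. The two distributions alone allow 12 to 22.
- *At least 12:* that many newly reached Grade 1 or more. Exactly 12 is possible if the 5 patients at Grade 1 and the 5 at Grade 2 stay put and the 12 end at Grades 1, 2, 3 and 4 in numbers 3, 2, 6 and 1.
- *At most 22:* the other 30 − 22 = 8 have highest grade 0. Exactly 22 is possible if the 5 at Grade 2 move to Grade 3, the 5 at Grade 1 move to Grade 2, and 12 from Grade 0 end at Grades 1 to 4 in numbers 8, 2, 1 and 1.

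**5. Highest grade against a worsening count.** Let b be the baseline prevalence of Grade 1 or more and w the probability of a new or worse grade. Both are assumed, and taken as independent; the baseline grade is taken to count in the period. The highest-grade rule expects n[1 − (1 − b)(1 − w)] patients and a worsening count expects nw, so the excess is n·b·(1 − w).
- b = 10%, w = 40%: 13.8 against 12.0, excess 1.8.
- b = 30%, w = 20%: 13.2 against 6.0, excess 7.2.
- b = 50%, w = 0: 15.0 against 0, excess 15.0.

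This shows how far apart the two quantities can lie. It is not the effect of excluding pre-dose samples: an abnormality that persists after dosing stays in the count.

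**6. Which parameters are exposed.**
- *Hemoglobin:* entry requires at least 9.0 g/dL (Protocol 7.1) and the endpoint is below 8.0 g/dL. A pre-dose Grade 3/4 value needs a fall of more than 9.0 − 8.0 = 1.0 g/dL between screening and C1D1. Protocol 9.2 lists no hemoglobin criterion at C1D1, so this is possible but unlikely.
- *Neutrophils:* Day 1 dosing requires ANC of at least 1.5 × 10⁹/L (Protocol 9.2), and severe neutropenia is below 0.5 × 10⁹/L (SAP 8.1.4.1). A patient who meets the dosing criterion cannot bring it in.
- *Lymphocytes, glucose, electrolytes:* Protocol 7.1 sets no limit, so nothing caps the baseline grade.

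**The case against.** A reader might infer that pre-existing abnormalities are presented as treatment-emergent toxicity, and that Grade 3-4 rates are inflated by up to the baseline prevalence. The documents do not support that. The same sentence of SAP 9.3.2 requires the baseline grades to be shown, and it does not call the treatment-period column treatment-emergent. When the baseline sample lies in the period, subtraction gives the number newly reaching Grade 3-4 exactly.

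A reader might also infer that the main hematologic harms are distorted. The entry and dosing criteria make that unlikely for severe neutropenia and Grade 3/4 hemoglobin. SAP 8.1.4 already limits those endpoints to the treatment period, so only a same-day pre-dose value is at issue. The hepatic categories are already post-baseline.

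Three further points favor the plan:
- Clinically significant abnormal values are recorded as AEs (Protocol 11.3.5 and 17.2.1). AEs must be new or worse, and SAP 9.2.3 tabulates hematologic AEs by grade.
- The laboratory listings carry the grade of each value.
- Protocol 12.4.7.2 also reports the maximum grade without a worsening condition, the Table 1 chemistry endpoint is an abnormality rather than a worsening, and SAP 10 openly discloses the dropped summaries.

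These points stand and limit the consequence. They do not explain why a sample's draw day should decide whether it is on-treatment. Nor do they supply a summary of within-patient change: listings are not a table, and AE reporting of laboratory values depends on investigator judgment.

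**Conclusion.** The point holds as a moderate weakness in a descriptive safety table. As written, SAP 9.1 and 9.3.2 admit pre-dose C1D1 samples into the on-treatment maximum, depending on draw day. This departs from the SAP's rules for its other safety data. No planned table shows within-patient worsening.

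The size cannot be determined, because the documents give neither baseline prevalences nor the share of samples drawn on C1D1. If 1 to 6 of 30 patients had a Grade 3-4 value only in a pre-dose C1D1 sample, the treatment-period rate would rise by 3.3 to 20 points, with the same patients visible in the baseline column. The exposure is mainly in parameters without an entry limit. No sample size, power or PFS, response or OS result is touched, and no clinical management changes.

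**What to change.** 1. In SAP 9.3.2, take the highest grade only from samples after the first dose and within the treatment period, in line with the hepatic rule in 9.3.1 and the vital-sign rule in 9.4.1. Treat a C1D1 sample without a time as pre-dose, as Table 3 does, and leave it out of the maximum.
2. Keep the Grade 3-4 abnormality counts. Do not replace them with a count restricted to grades worse than baseline: that would drop persistent Grade 3-4 abnormalities from an endpoint defined by their presence.
3. Replace or supplement the two separate distributions with a shift table of baseline grade by worst post-baseline grade, including a missing category.
4. In SAP 8.1.4.2, state that hemoglobin values are post-first-dose.

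The data are already collected. The cost is a few lines of SAP text and one table layout, and on-treatment counts may be slightly lower.
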